11. AE and laboratory safety evaluations will be performed according to NCI CTCAE v5.0. Refer to Section 8 for AE and SAE definitions, recording, determination of causal relationship, severity, reporting deadlines, and processing. C1D8 AE evaluation will be conducted via phone.
12. Tumor evaluations will be performed based on RECIST v1.1 and the same imaging method (CT/MRI) should be used for the same subject during the trial. Baseline evaluation will be conducted within 28 days prior to enrollment. After the first dose of study treatment, tumor imaging evaluation will be performed once Q6W (\pm 7 days) and Q9W (\pm 7 days) starting from Cycle 7, until initiation of a new anti-tumor therapy, PD (assessed at 12W or after), withdrawal of informed consent, lost to follow up, completion of treatment, or death. If the subject has confirmed or suspected bone metastatic lesion presents at baseline, a PET scan with contrast can be used for imaging evaluation. For subjects who discontinue the treatment for reasons other than imaging-confirmed PD, if the subject's last imaging evaluation is greater than 4 weeks prior to discontinuation, the imaging evaluation should be performed at the end-of-study treatment visit and be reperformed Q12W (\pm 7 days) thereafter until one of the followings occurs: start of new anti-tumor therapy, PD, withdrawal of informed consent, lost to follow-up or death.
13. Sintilimab: 200 mg, IV Q3W, for up to 24 months (starting from the first dose), or until PD, death, intolerable toxicity, withdrawal of informed consent, completion of treatment, or any other investigator-determined reason for treatment discontinuation. Treatment can be delayed for up to 1 week if the administration day is on a holiday. The study treatment can be administered 3 days before or 3 days after the scheduled day of administration.
14. Quality of life evaluation: on the day of the first dose, during each imaging evaluation, including EQ 5D-5L, EORTC QLQ-C30. PRO-CTCAE™ will be administered day 1 of every cycle, and during the first safety follow up.
15. Subjects are required to provide at least 20 slices of archived or fresh tumor tissue samples during screening for biomarkers. If not available, a fresh biopsy will be performed. Optional biopsy at C3D1 \pm 7 days, and when PD is confirmed.

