3.1 Overall Design

This is a Phase 2 clinical trial evaluating the efficacy and safety of sintilimab in subjects with UPS. Subjects with unresectable, locally advanced, recurrent or metastatic UPS will be enrolled. A total of 25 evaluable subjects will be enrolled and treated. Subjects will be treated with sintilimab (200 mg IV on Day 1 Q3W). The treatment will be repeated every 3 weeks until progressive disease (PD), intolerable toxicity, initiation of new anti-tumor therapy, withdrawal of informed consent, lost to follow-up, completion of therapy, death, or any other investigator-determined reasons for treatment discontinuation (whichever occurs first). Treatment will be infused for a maximum period of up to 24 months (starting from the first dose). During the trial, tumor imaging evaluation will be initially performed once Q6W (\pm 7 days) and Q9W (\pm 7 days) starting from Cycle 7, and will be based on RECIST 1.1, until PD (assessed at 12W or after), initiation of new anti-tumor therapy, withdrawal of informed consent, lost to follow-up, death, or completion of the study (whichever comes first). After the completion or discontinuation of the

study treatment, safety follow-up (30 days \pm 7 days and 90 days \pm 7 days after the last dose) and survival follow-up (every 60 days \pm 7 days) will be performed. The primary endpoints of the trial will be confirmed ORR per RECIST v.1.1.

Figure 1 Schematic of SiARa-UPS study design and administration

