6.2.6 Survival follow-up

After completing the safety follow-ups, the subject should be contacted (telephone visits are allowed) once every 60 days (\pm 7 days) to obtain the survival information, any subsequent systemic anti-tumor therapy, and PD information. Long-term follow-up should be continued until death or 3 years after last patient enrolled.

Subsequent anti-tumor therapy

The investigator or qualified designee will collect all the information about new anti-tumor therapies initiated after the last dose of the study drugs and the corresponding efficacy. If the subject initiates a new anti-tumor therapy within 30 days after the last dose, then the safety follow-up must be performed before initiation of the new therapy.

The subject should be followed for survival after initiation of a new anti-tumor therapy. Refer to Section [6.2.6](#) – Survival follow-up for details regarding survival follow-up.

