7.1.2 Tumor imaging during the study

The imaging method used for the evaluation of tumor burden during each visit should be the same as the one used at baseline. Other affected sites should be examined based on the signs and symptoms of each subject. Baseline evaluation will be conducted within 28 days prior to the first dose of the study treatment, which means the investigator can evaluate the imaging results within 28 days prior to the enrollment.

After the first dose of study treatment, tumor imaging evaluation will initially be performed once Q6W (\pm 7 days) and Q9W (\pm 7 days) starting from Cycle 7, until initiation of a new anti-tumor

therapy, PD (at 12W or after), withdrawal of informed consent, lost to follow-up, death, or completion of the study (whichever comes first).

Patients who have radiographic PD will be allowed to continue therapy if clinically stable till next scheduled scans. If PD is confirmed on the next scan, patient will discontinue therapy. For certain cases which PD cannot be determined, especially on those with equivocal non-target lesions enlargement or equivocal new lesions, the treatment may be continued until signs of clinical instability develop or when PD is confirmed by the investigator in the next scheduled scan. Once PD is confirmed, the disease progression date will be recorded as the date when the suspected PD was initially observed. Definition of clinical stability is as follows:

- Absence of clinically significant signs and symptoms suggesting PD (including worsening laboratory values);
- No reduction in ECOG PS score;
- No rapid PD;
- Absence of rapid progression of disease or progressive tumor at critical anatomical sites (e.g. spinal cord compression) that requires urgent medical interventions.

Tumor evaluations should be performed as scheduled and should not be delayed due to treatment delays, holidays, or any other reasons.

Further tumor evaluations are not required for subjects who discontinue the treatment due to radiographic PD.

For subjects who discontinue the treatment for reasons other than radiographic PD, tumor evaluation should be performed Q12W (\pm 7 days) until one of the followings occurs: start of new anti-tumor therapy, PD, withdrawal of informed consent, or death. A scan at the end of the treatment is not mandatory if it were less than 4 weeks after the last tumor evaluation.

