9.3.1.2 Design and sample size/power

The primary efficacy endpoint will be confirmed ORR at 12W. A patient will be considered as a responder to the treatment if he/she has achieved confirmed complete response (CR) or partial response (PR) determined by RECIST 1.1.

A Simon's two-stage Minimax design will be used to monitor the efficacy of sintilimab. The null hypothesis involves an ORR of 10% that will be tested against an ORR of 30%, i.e. a 20% improvement. In the first stage, 15 patients will be treated. If there is ≤ 1 patient who achieves objective response in these 15 patients, the study will be terminated. If the study moves forward to second stage, an additional 10 patients will be treated leading to a total of 25 patients. Six or more responders out of the 25 treated patients will be considered clinically relevant to justify further investigation. The power of this design is 80% under the 1-sided type I error rate of 5%. The early stopping probability is 55% if the ORR is 10% and the average sample size would be 19.5. Assuming a 5% dropout rate, we will need to enroll up to a total of 27 patients.

Analysis of key and other secondary efficacy endpoints

The key secondary efficacy endpoints are ORR (RECIST 1.1), DCR, DOR, PFS and OS in the evaluable and ITT populations.

The ORR, DCR and corresponding exact 95% CIs of the sintilimab arm will be estimated using binomial distribution.

PFS is the time from first dose to first date of Investigator-determined progression (by imaging),

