or to death due to any cause. OS is the time from first dose to death due to any cause. Subjects who neither progress nor die will be censored at the date of their last tumor imaging evaluation. Subjects who do not have any tumor imaging evaluation after baseline will be censored on the date of first dose. The mPFS and mOS and corresponding 95% CI will be estimated via the Kaplan-Meier method, and survival curves will be plotted [13]. Log-rank test will be performed to test the difference in survival between groups [14]. Regression analyses of survival data based on the Cox proportional hazards model [15] will be conducted on PFS or OS. The proportional hazards assumption will be evaluated graphically and analytically, and regression diagnostics (e.g., martingale and Schoenfeld residuals) will be examined to ensure that the models are appropriate. For repeated measures, linear mixed model will be used for continuous outcomes and GEE model will be fit for binary outcomes [16]. Appropriate methods will be applied to analyze correlative data. Other statistical analyses may be performed as appropriate.

DoR: subjects who have achieved CR or PR: from first date of Investigator-determined response to Investigator-determined PD or death; subjects who neither progress nor die: be censored at the date of their last tumor imaging evaluation. The mDoR will be estimated via the Kaplan-Meier method and survival plots will be presented.

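### PFS and DoR run past the start of a new anti-tumor therapy although protocol imaging stops there, so the handling of a switch depends on what happens later

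*Combined protocol and SAP*

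**What the plan says.** **Scans.** Note 12 to the schedule of visits (Table 1) runs imaging "until initiation of a new anti-tumor therapy, PD (assessed at 12W or after), withdrawal of informed consent" and some further stops. Section 3.1 has the same stop: "until PD (assessed at 12W or after), initiation of new anti-tumor therapy, withdrawal of informed consent". For subjects who end treatment without radiographic PD, Section 7.1.2 continues 12-weekly scans "until one of the followings occurs: start of new anti-tumor therapy, PD, withdrawal of informed consent, or death". On every schedule, a new therapy ends the scans.

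**Endpoints.** Section 9.3.1.2: "PFS is the time from first dose to first date of Investigator-determined progression (by imaging", "or to death due to any cause". The censoring rule is "Subjects who neither progress nor die will be censored at the date of their last tumor imaging evaluation"; subjects with no scan after baseline are censored at first dose. DoR runs from first response to PD or death, with the same last-scan censoring for event-free responders. Neither definition mentions new therapy.

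**Follow-up.** Under Section 6.2.6, subjects are contacted every 60 days "to obtain the survival information, any subsequent systemic anti-tumor therapy, and PD information", until death or three years after the last enrolment. This continues after a new therapy starts. Appendix 3, Section 2.4, says a protocol must state how new therapy before progression affects best response. This protocol states no such rule for response, PFS or DoR.

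**The concern.** The plan stops looking at the switch but goes on counting. Someone who leaves sintilimab without documented PD (for toxicity, clinical deterioration or by choice) and starts another drug has no further scheduled scans. If that person dies a year later, the whole interval counts as progression-free and is credited to sintilimab.

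PFS and DoR are named as key secondary endpoints, and the study hypothesis in Section 1.1.2 is durable response. With one arm, readers will set the results beside the 3-month median PFS cited in that section.

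**Working it through.** **1. The plan's own figures.** None is stated for PFS or DoR. The ORR design reproduces: power at 30% is 0.802; attained one-sided alpha at 10% is 0.033, under the 5% ceiling; early stopping is 0.549; average size is 15 + (1 − 0.549) × 10 = 19.5; enrolment is 25/0.95 = 26.3, so 27. It counts responders and does not use the PFS or DoR event rule.

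**2. What the rule does to subjects who switch before documented PD.**

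| Later course | As written |
|---|---|
| Dies, no PD recorded | Event at death |
| PD reported at a contact | Event at that PD |
| Neither recorded | Censored at last scan |

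Example with assumed dates: last scan at week 12 (2.8 months), switch at 3.5, death at 14.0. As written, PFS is an event at 14.0 months, of which 14.0 − 2.8 = 11.2 are unscanned and 14.0 − 3.5 = 10.5 follow the switch. A second subject with the same scan and switch dates but no later event is censored at 2.8.

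**3. Illustration of size.** Inputs:
- Time to PD exponential, median 3 months (expanded cohort, Section 1.1.2).
- Survival after PD exponential, median 8 or 14 months (assumed). With a = ln2/3 and b = ln2/8 or ln2/14, median OS solves (a·e^(−bt) − b·e^(−at))/(a − b) = 0.5, giving 12.7 and 18.7 months, inside the 12-20 of Section 1.1.1.
- Scans at weeks 6, 12 and 18, then every 9 weeks; 36-month cut-off.
- 10-30% switch, at a uniformly distributed time before PD (assumed).
- PD on the next therapy at a median of 4 months (assumed), of which none, half or all is captured.

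Kaplan-Meier PFS from 200,000 simulated subjects per scenario, 20% switching, shown as 6-month / 12-month in percent (ranges cover the two post-PD survival assumptions):

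| Later PD captured | As written | Censored at last prior scan | Switch as event |
|---|---|---|---|
| None | 45.5-46.5 / 16.7-17.8 | 41.2-41.8 / 10.6 | 31.7-32.1 / 7.4 |
| Half | 41.9-42.9 / 13.1-14.0 | 41.0-41.5 / 10.6-10.7 | 31.5-31.9 / 7.5 |
| All | 38.6-39.5 / 9.7-10.3 | 41.1-41.4 / 10.6-10.7 | 31.6-31.9 / 7.3-7.5 |

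With imaging continued through the switch, and PD timing unaffected by it, the figures are about 37 / 9. Mean time from switch to the counted event is 11.4-13.9 months with no capture and 4.3-4.8 with full capture.

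**Median.** At 10% and 20% switching it is 4.1 months both as written and censored, at every capture level. It sits on the week-18 scan: 18 × 7/30.4375 = 4.14. At 30% with no capture it is 5.7-6.2 as written against 4.1 censored; with half or full capture it is 4.1 under both.

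**4. A slower disease course.** With a median of 7 months (first 10 patients, Section 1.1.2) and 20% switching, 12-month PFS as written against censored is 41.5-42.3 against 39.7-39.8 (no capture), 37.7-38.4 against 39.6-39.9 (half) and 34.3-34.5 against 39.8-39.9 (all). The median with no capture is 9.4-10.2 against 8.3. With full capture the as-written curve can also fall slightly below continued imaging, where 0.5^(10.35/7) = 0.36 are still free of PD at the week-45 scan. That comes from assuming earlier PD on the next drug than the subject would otherwise have had.

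**5. DoR, invented times.** Five responders have events at 3, 4, 6, 8 and 10 months. The sixth has a last scan at 2, switches at 2.5 and dies at 18. The median is 6 as written, 6 censored at the last scan, and 4 with the switch as an event.

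**The case against.** Several points on the other side stand.

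- A reader might infer that PFS is always inflated by a fixed amount. The largest gaps need no PD to be recorded after the switch, whereas Section 6.2.6 collects PD information and the efficacy of later therapies. With full capture the gap to censoring closes or reverses.
- A reader might infer that every switcher's unscanned time is counted. Switchers with no later event are already censored at the last scan.
- Section 9.3.1.2 plans medians and curves, not 6- or 12-month rates, and the median often does not move.
- The switching share is not in the documents. Note 12 to Table 1 asks for an end-of-treatment scan if the last is over 4 weeks old, and Appendix 3, Section 2.4.4, urges documenting progression after discontinuation. Both should reduce the share, so 20-30% may be pessimistic.
- At 25 subjects, a 40% rate has a 95% half-width of 1.96 × √(0.4 × 0.6/25) = 19 points, wider than any shift at 20% switching shown above.
- Censoring at the switch may be informative: it gives about 41% at 6 months against 37% with continued imaging.

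The defence that following subjects through later therapy is a legitimate treatment-policy choice does not stand. That choice needs scans to continue after the switch, and here they stop. Sampling error is no answer either: the confidence interval will display it, but will not display this distortion.

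**Conclusion.** The defect holds as a stated rule that misbehaves when followed. Imaging ends at the switch, later events still count, and two subjects who switch on the same day are handled differently according to what happens afterwards.

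The PFS curve lies above the one that counts the switch as an event. With a 3-month median time to PD it also lies above the one with continued imaging. Against censoring at the last prior scan, direction and size rest on unscheduled capture of later PD: at 20% switching, 6-7 points too high at 12 months with none captured, about 3 with half, and equal or slightly lower with all. The median rises to about 6 against 4 months only near 30% switching with no capture. These median results assume the 3-month course; at 7 months a shift appears at 20%.

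The documents do not support a claim that DoR is inflated by a known amount: the one worked example gives the same median as written and censored. Nor do they support a claim that the trial's conclusion is at risk, since PFS and DoR carry no success threshold and the go/no-go rule is on ORR alone. The plan should be changed, but the primary result does not depend on it.

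**What to change.** In the PFS and DoR paragraphs of Section 9.3.1.2, state that a subject who starts a new systemic anti-tumor therapy before documented PD is censored at the last tumor assessment on or before that start, and that later PD or death is not a PFS or DoR event. The existing first-dose rule covers a PFS subject with no earlier post-baseline scan. Define which therapies count, including how the local treatments allowed in Section 5.4 are classed. OS is unchanged.

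Report two sensitivity analyses: new therapy as an event on its start date, and the rule as currently written.

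The cost is a few sentences and two extra runs; subsequent therapy is already collected (Table 1, Section 6.2.6). The price is slightly fewer events and possibly informative censoring that leaves the estimate somewhat high. The analysis with the switch as an event bounds this from below.

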9.2 Statistical Analysis Population

Intention-to-treat set (ITT): all enrolled subjects who are treated.

Evaluable set (EP): all enrolled subjects who have measurable lesions at baseline and have at least one restaging evaluation. This analysis set is used for ORR analysis.

Safety analysis set (SS): all subjects who received at least one dose of study treatment. The SS is used for all the safety evaluations.

Per-protocol set (PPS): A subset of ITT, refers to subjects who do not have major protocol violations that affect the efficacy evaluation. The PPS is used for the sensitivity analyses of primary efficacy endpoints and key secondary efficacy endpoints.

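### PFS and OS share censoring rules built only on scans: read literally, ITT patients who die unscanned are censored at day 1, and OS has no last-known-alive rule

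*Combined protocol and SAP*

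**What the plan says.** All the relevant rules stand in section 9.3.1.2, under the sub-heading on key and other secondary efficacy endpoints.

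- PFS runs from first dose to investigator-determined progression on imaging or death from any cause. For OS, "OS is the time from first dose to death due to any cause".
- Two censoring sentences follow directly. The first is "Subjects who neither progress nor die will be censored at the date of their last tumor imaging evaluation". The second is "Subjects who do not have any tumor imaging evaluation after baseline will be censored on the date of first dose". Neither names an endpoint, and the next sentence estimates median PFS and median OS together.
- DoR has its own censoring rule further down. No other PFS or OS censoring rule appears in the document.
- On populations: "The key secondary efficacy endpoints are ORR (RECIST 1.1), DCR, DOR, PFS and OS in the evaluable and ITT populations". Section 9.2 defines ITT as everyone enrolled and treated. The evaluable set is "all enrolled subjects who have measurable lesions at baseline and have at least one restaging evaluation".
- On follow-up, section 7.1.2 states: "Further tumor evaluations are not required for subjects who discontinue the treatment due to radiographic PD". For those who stop treatment for other reasons, scans continue "until one of the followings occurs: start of new anti-tumor therapy, PD, withdrawal of informed consent, or death". Survival contact is separate: every 60 days under section 6.2.6, where "Long-term follow-up should be continued until death or 3 years after last patient enrolled".

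**The concern.** A censoring rule tied to scans suits PFS. OS is followed by contact, whether or not the patient is scanned. Applying the scan rules to both endpoints has three consequences.

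(a) The first sentence excludes patients who die; the second does not. A treated patient who dies before any scan is therefore censored at day 1 for both endpoints. An unscanned patient known to be alive months later also loses all OS follow-up. The evaluable set excludes unscanned patients by definition, so ITT is the only analysis that can count these deaths, and the literal rule removes them there. ITT PFS and OS are then biased upward.

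(b) A living, progression-free patient is cut at the last scan for OS, although survival contact may continue after it.

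(c) A patient alive after progression fits neither sentence, so OS has no censoring date for that group. An analyst must supply one. The only model in the text is the last scan, which would discard follow-up after progression and bias OS downward.

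The errors run in opposite directions, so the reported OS would depend on choices the plan does not record. In a single-arm, open-label trial those choices should be fixed before the data are seen.

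**Working it through.** **1. The rules applied to OS in ITT**

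| Patient | Sentence that applies | OS under the text | OS by its definition |
|---|---|---|---|
| Dies before any scan | No-imaging | Censored day 1 | Event at death |
| Alive, never scanned | No-imaging | Censored day 1 | At risk to last contact |
| Alive, scanned, no progression | Last-imaging | Censored at last scan | At risk to last contact |
| Alive after progression | Neither | No date given | At risk to last contact |
| Dies after a scan | Neither | Event | Event |

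The first row also applies to PFS. The plan states no power or precision figure for PFS or OS, so there is none to reproduce.

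**2. Deaths before the first scan (a)**

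Inputs: median survival 12 to 20 months in advanced soft tissue sarcoma (section 1.1.1); median PFS 3 months in the expanded pembrolizumab cohort (section 1.1.2); first scan at week 6 ± 7 days; 25 patients. Exponential survival is an assumption.

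6 weeks = 42/30.44 = 1.38 months. P(death by week 6) = 1 − 0.5^(1.38/median):

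- Median 12: 1 − 0.5^(1.38/12) = 7.7%; × 25 = 1.9 patients.
- Median 20: 1 − 0.5^(1.38/20) = 4.7%; × 25 = 1.2 patients.
- Across weeks 5 to 7: 1.0 to 2.2 patients.
- Chance of at least one such death by week 6: 86% (median 12) or 70% (median 20).

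**3. Effect on the estimates (a)**

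Patients censored at day 1 leave the risk set before any event. The curve then estimates S(t)/S(1.38), and under a constant hazard the median moves from m to m + 1.38.

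- Median OS: 12 to 13.4 months; 20 to 21.4 months.
- 6-month OS: 0.707/0.923 = 77% instead of 71%; 0.812/0.953 = 85% instead of 81%.
- Median PFS = 3 × ln(0.5 × (1 − q))/ln(0.5), where q is the proportion dying unscanned: q = 4.7% gives 3.2 months and q = 7.7% gives 3.3 to 3.4 (3.35).

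Sensitivity: if ECOG 0–1 and expected survival of at least 12 weeks halve the hazard before week 6 (assumption), q is 3.9% or 2.4%, which is 1.0 or 0.6 of 25 patients. Median OS then moves from 12.7 to 13.4 or from 20.7 to 21.4 months (+0.7), and median PFS from 3 to 3.1–3.2.

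A Kaplan-Meier simulation at n = 25 (4,000 runs; assumed 18-month accrual and 36 months of further follow-up), changing only the day-1 rule, agrees. Twelve-month OS is 49.9% with deaths counted and 54.1% under the literal rule when the true median is 12 months. The figures are 66.1% and 69.3% when it is 20.

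**4. Cutting at the last scan (b) and (c)**

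Large-sample simulation (N = 400,000). Assumptions, none from the plan: 20% of patients have durable control with median PFS 40 months and the rest 2.6 months; 15% of PFS events are deaths; median survival after progression is 9 or 14 months; accrual takes 18 months. Scans are at weeks 6, 12 and 18, then every 9 weeks to 24 months, then every 12 weeks.

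- (b) only, analysed 36 months after last enrolment, 9-month post-progression case: median OS 14.0 v 14.0 months; 36-month OS 18.9% v 19.0%. If 25% of progression-free patients stop scans for new therapy at 3 to 24 months (assumption), 36-month OS is 17.5% v 19.0%.
- (c) with every living patient cut at the last scan:

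| Survival after progression (median) | OS to last contact | Last scan, 12 months after last enrolment | Last scan, 36 months after |
|---|---|---|---|
| 9 months | 14.0 | 11.6 | 13.6 |
| 14 months | 19.0 | 13.3 | 17.1 |

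Repeat runs agree to within about 0.1 month.

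**The case against.** The strongest reply is that the paragraph should be read as a whole. Both definitions end at death from any cause, and censoring opens with patients who neither progress nor die. The no-imaging sentence can be taken to cover members of that group who have no scan date to use, so an unscanned death stays an event. The opening condition is itself a PFS condition, since progression is not an OS event, and DoR repeats it. Survival contact every 60 days, with death dates and OS listed for all subjects (section 9.3.5), makes last contact the natural choice for OS.

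This reading is plausible, and a careful analyst may well adopt it. It is not in the text, however: nothing says that death takes precedence or that the sentences are for PFS only. If it is accepted, OS is left with no censoring date at all.

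On size, several points stand:

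- The figures for (a) lean high. They treat every death before week 6 as unscanned, although section 6.2.7 allows unscheduled imaging, and they apply a constant hazard to selected patients.
- Effect (b) is negligible while scans continue.
- The losses in (c) come from a rule the plan does not state, and the largest come from an analysis time it does not schedule.
- With 25 patients, the 95% sampling range of the median is roughly 6 to 20 months when the truth is 12. A shift of 0.7 to 1.4 months is small beside that, though it is systematic.
- PFS and OS carry no hypothesis or threshold.

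**Conclusion.** The concern holds. As written, the rules censor unscanned ITT deaths at day 1, against the plan's own definitions, and give OS no last-known-alive rule. The absence of that rule is certain from the text. Whether unscanned deaths would actually be censored depends on how literally the analyst reads the second sentence.

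Under the literal reading, one to two deaths among 25 would probably be lost. Median OS would be overstated by about 1.4 months (0.7 with a halved early hazard) and a 3-month median PFS by 0.1 to 0.4 months. These figures rest on exponential survival and the medians quoted in the background. Part (b) adds little. Part (c) could lower median OS by 0.4 to about 2 months at 36 months after last enrolment, under assumed inputs, if the gap were filled with the last scan.

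The primary response test, the two-stage design, the sample size and DoR are not affected. Because PFS and OS are key secondary endpoints in ITT, this should be fixed before analysis.

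**What to change.** Replace the two shared sentences with separate rules.

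- **OS:** death from any cause is an event on the date of death. All other patients are censored at the last date known alive from any contact, regardless of imaging or progression.
- **PFS:** death without a prior scan is an event on the date of death. Patients alive without progression are censored at the last scan, or at day 1 only if alive with no post-baseline scan.

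The cost is a few sentences of analysis-plan wording. Survival status and death dates are already collected, so no visit, scan or data field is added.
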